End of Treatment (EOT)	The date the last dose of study drug was taken by the enrolled subject. In this study, the end of treatment is a maximum of 84 days for invasive aspergillosis subjects or 180 days for invasive mucormycosis subjects.
Endpoint	Variable that pertains to the efficacy or safety evaluations of a trial.
Enroll	To register or enter a subject into a clinical trial. Note: Once a subject has received the study drug, the clinical trial protocol applies to the subject.
Evaluable Subject	A subject who has received at least one dose of study drug.
Intervention	The drug, device, therapy or process under investigation in a clinical study that is believed to have an effect on outcomes of interest in a study. (e.g., health-related quality of life, efficacy, safety and pharmacoeconomics).
Screen failure	Potential subject who did not meet 1 or more criteria required for participation in a trial.
Screening	A process of active consideration of potential subjects for enrollment in a trial.
Screening period	Period of time before entering the investigational period, usually from the time when a subject signs the consent until just before the test drug is given to a subject.
Study period	Period of time from the first site initiation date to the last site completing the study.
Variable	Any entity that varies; any attribute, phenomenon or event that can have different qualitative or quantitative values.

IV. SYNOPSIS

Date and Version # of Protocol Synopsis:	05 Sep 2019 / Version 4.0
Sponsor: Astellas Pharma Global Development Inc. (APGD)	Protocol Number: 9766-CL-0107
Name of Study Drug: Isavuconazonium sulfate	Phase of Development: 2
Title of Study: A Phase 2, Open-Label, Non-Comparative, Multicenter Study to Evaluate the Safety and Tolerability, Efficacy and Pharmacokinetics of Isavuconazonium Sulfate for the Treatment of Invasive Aspergillosis (IA) or Invasive Mucormycosis (IM) in Pediatric Subjects	
Planned Study Period: From 1Q2019 to 1Q2021	
Study Objective(s): Safety Objective To evaluate the safety and tolerability of isavuconazonium sulfate in pediatric subjects Efficacy Objective To assess the efficacy of isavuconazonium sulfate for the treatment of invasive aspergillosis (IA) or invasive mucormycosis (IM) in pediatric subjects Pharmacokinetic Objective To evaluate the pharmacokinetics of isavuconazole by monitoring the plasma concentrations in pediatric subjects during treatment with isavuconazonium sulfate	

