2. Follow-up is to be completed 30 (\pm 7) and 60 days (\pm 7) post-last dose from day 84 or EOT for IA subjects, and may be performed via telephone at the discretion of the investigator.
3. Diagnosis must be completed within 10 days of first dose.
4. Height is to be collected at baseline only. Weight is to be taken at baseline and day 84 or EOT.
5. Vital signs are to be measured within 1 hour prior to and approximately 1 hour after the end of each infusion. No additional vital signs are needed on dosing days for oral administration.
6. 12-lead ECG will be performed prior to study drug administration on each scheduled day.
7. Record assessments that are performed during the study to document response to antifungal therapy (e.g., serum galactomannan, radiology, mycological tests, changes in clinical signs and symptoms and any surgical procedure).
8. Pharmacokinetic trough samples should ideally be drawn immediately prior to the next dose of study drug, but must be taken no earlier than 1 hour prior to the next dose on days 7, 14, 21, 42 and 84 or EOT.
9. For both intravenous and oral dosing: 24-hour pharmacokinetic samples will be obtained on any one day between day 14 and day 42, while the subject is still receiving study drug, for subjects who consent to participation in the 24-hour pharmacokinetic assessment. The intravenous pharmacokinetic samples will be collected as follows: within 1 hour prior to the start of the intravenous isavuconazonium sulfate infusion. This sample will be the same as the trough sample prior to dose, if it coincides with scheduled days 14, 21 or 42, and immediately after the completion of the intravenous infusion (no more than 5 minutes after); and within 4 to 10 hours after the start of the intravenous infusion and within 16 to 24 hours after the start of the intravenous infusion (must be obtained before the start of the next infusion).
The oral pharmacokinetic samples will be collected as follows: within 1 hour of the next oral dose (this sample will be the same as the trough sample prior to dose, if it coincides with scheduled days 14, 21 or 42); 1 hour post dose (\pm 10 minutes); 3 hours post dose (\pm 10 minutes); 4 hours post dose (\pm 10 minutes); within 6 to 8 hours (\pm 30 minutes) of study drug administration; and 24 hours (within 1 hour before next study drug administration) after study drug administration.
10. Clinical (safety) laboratory samples will be assessed by the local laboratory.

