11. Hepatic panels will be collected at baseline, day 3, day 7 and then weekly thereafter while subjects are receiving study drug.
12. Pregnancy testing not applicable for male subjects. Not necessary for female subjects who are of non-childbearing potential (e.g., premenarchal in the judgment of the investigator on day 1 and throughout the study treatment, or documented surgically sterile). Pregnancy testing may be urine or serum, dependent upon institutional standard of care.
13. Concomitant medications are to be captured during the study and only related to AE's during the 30- and 60-day follow-up period.
14. All AEs must be monitored until symptom resolution or until the condition stabilizes.
15. For both intravenous and oral dosing: Loading doses on days 1 and 2 will be administered every 8 (\pm 2) hours. The first maintenance dose should start 12 to 24 hours after the administration of the last loading dose. Subsequent maintenance doses will be administered once daily (24 \pm 2 hours from the previous maintenance dose). Subjects who are discharged from the hospital with oral capsules for at-home administration must return weekly to receive new oral dosing supplies. Return visits should coincide with days when study-related assessments are required. Oral dosing is allowed for subjects 6 to $<$ 18 years of age and with a body weight of at least 12 kg.

Footnotes continued on next page

16. Subjects who begin oral administration are to complete the oral dosing acceptability assessment after ingesting their first oral dose.
17. All-cause Mortality will be assessed on days 42 and 84 or EOT.

Table 2 Extended Schedule of Assessments (IM Subjects) – Day 85 through Day 180 and IM Follow-up (30 and 60 days Post-Day 180 [Last Dose of Study Drug])

Period	Treatment				Follow-up ²		
	Day	85	115	145	180/IM or EOT ¹	210 (30 Day) IM or EOS	240 (60 Day) IM or EOS
Visit window (days)	± 2	± 2	± 2	± 7	± 7	± 7	± 7
ASSESSMENTS							
Physical examination					X		
Weight					X		
Vital signs ³	X	X	X	X			
Routine 12-lead ECG ⁴	X	X	X	X			
Efficacy response assessment ⁵	◀					▶	
Clinical laboratory tests (chemistry, hematology, hepatic panel, INR) ⁶		X	X	X			
Pregnancy test ⁷					X		
Prior and concomitant medications ⁸	◀					▶	
AE ⁹	◀					▶	
Isavuconazonium sulfate dosing ¹⁰	X	X	X	X			
Oral dosing acceptability assessment	X ¹¹						
Mortality Status ¹²					X		

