7.5 Analysis of Safety

7.5.1 Adverse Events

AEs will be coded using MedDRA.

TEAE is defined as an AE observed after starting administration of the study drug through 30 days after the last dose. The number and percentage of subjects with treatment-emergent AEs, SAEs, AEs leading to withdrawal of treatment and AEs related to study drug will be summarized by MedDRA system organ class, MedDRA preferred term for overall subjects and by subjects in each cohort. The number and percentage of AEs by severity will also be summarized. All AEs will be listed.

A study drug-related TEAE is defined as any TEAE with a causal relationship of YES by the investigator.

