12.5 Liver Safety Monitoring and Assessment

Any subject enrolled in a clinical study with active drug therapy and reveals an increase of serum aminotransferases (AT) to $> 3 \times \text{ULN}$ or bilirubin $> 2 \times \text{ULN}$ should undergo detailed testing for liver enzymes (including at least ALT, AST, alkaline phosphatase [ALP] and TBL). Testing should be repeated within 72 hours of notification of the test results. For studies for which a central laboratory is used, alerts will be generated by the central laboratory regarding moderate and severe liver abnormality to inform the investigator and study team. Subjects should be asked if they have any symptoms suggestive of hepatobiliary dysfunction.

Definition of Liver Abnormalities

Confirmed abnormalities will be characterized as moderate and severe where ULN:

	ALT or AST		TBL
Moderate	$> 3 \times \text{ULN}$	or	$> 2 \times \text{ULN}$
Severe	$> 3 \times \text{ULN}$	and	$> 2 \times \text{ULN}$

In addition, the subject should be considered to have severe hepatic abnormalities for any of the following:

- ALT or AST $> 8 \times \text{ULN}$.
- ALT or AST $> 5 \times \text{ULN}$ for more than 2 weeks.
- ALT or AST $> 3 \times \text{ULN}$ and International Normalized Ratio (INR) > 1.5 (If INR testing is applicable/evaluated).
- ALT or AST $> 3 \times \text{ULN}$ with the appearance of fatigue, nausea, vomiting, right upper quadrant pain or tenderness, fever, rash and/or eosinophilia ($> 5\%$).

The investigator may determine that abnormal liver function results, other than as described above, may qualify as moderate or severe abnormalities and require additional monitoring and follow-up.

Follow-up Procedures

Confirmed moderate and severe abnormalities in hepatic functions should be thoroughly characterized by obtaining appropriate expert consultations, detailed pertinent history, physical examination and laboratory tests. The site staff is to complete the liver abnormality case report form (LA-CRF). Subjects with confirmed abnormal liver function tests (LFTs) should be followed as described below.

Confirmed moderately abnormal LFTs should be repeated 2 to 3 times weekly then weekly or less if abnormalities stabilize or the study drug has been discontinued and the subject is asymptomatic.

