Severe hepatic liver function abnormalities as defined above, in the absence of another etiology, may be considered an important medical event and may be reported as a SAE. The sponsor should be contacted and informed of all subjects for whom severe hepatic liver function abnormalities possibly attributable to study drug are observed.

To further assess abnormal hepatic laboratory findings, the investigator is expected to:

- Obtain a more detailed history of symptoms and prior or concurrent diseases. Symptoms and new-onset diseases is to be recorded as “AEs” within the eCRF. Illnesses and conditions such as hypotensive events, and decompensated cardiac disease that may lead to secondary liver abnormalities should be noted. Nonalcoholic steatohepatitis is seen in obese hyperlipoproteinemic and/or diabetic subjects, and may be associated with fluctuating AT levels. The investigator should ensure that the medical history form captures any illness that predates study enrollment that may be relevant in assessing hepatic function.
- Obtain a history of concomitant drug use (including nonprescription medication, complementary and alternative medications), alcohol use, recreational drug use and special diets. Medications, is to be entered in the eCRF. Information on alcohol, other substance use and diet should be entered on the LA-CRF or an appropriate document.
- Obtain a history of exposure to environmental chemical agents.
- Based on the subject’s history, other testing may be appropriate including:
 - Acute viral hepatitis (A, B, C, D, E or other infectious agents),
 - Ultrasound or other imaging to assess biliary tract disease,
 - Other laboratory tests including INR, direct bilirubin.
- Consider gastroenterology or hepatology consultations.
- Submit results for any additional testing and possible etiology on the LA-CRF or an appropriate document.

Study Treatment Discontinuation

In the absence of an explanation for increased LFT’s, such as viral hepatitis, preexisting or acute liver disease or exposure to other agents associated with liver injury, the subject may be discontinued from study treatment. The investigator may determine that it is not in the subject’s best interest to continue study treatment. Discontinuation of study treatment should be considered if:

- ALT or AST $> 8 \times$ ULN.
- ALT or AST $> 5 \times$ ULN for more than 2 weeks.

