6.5.1 Adverse Events

TEAE is defined as an AE observed after starting administration of the study drug through 30 days after EOT. The number and percentage of subjects with treatment-emergent AEs, serious adverse events (SAEs), AEs leading to withdrawal of treatment, and AEs related to study drug will be summarized by MedDRA system organ class, MedDRA High Level term, and MedDRA preferred term for overall subjects and by subjects in each age cohort. The number and percentage of AEs by severity will also be summarized. All AEs will be listed.

A study drug-related TEAE is defined as any TEAE with a causal relationship of YES by the investigator. The incidence of treatment emergent AEs will be summarized by relationship to study drug and severity for all subjects and by each age cohort. The protocol defines how Treatment Emergent AEs are determined. Although all AEs are collected, the summary Table will be based on the TEAEs.

Clinically significant out-of-range laboratory findings are to be determined and documented by the investigator/subinvestigator who is a qualified physician. Clinically significant changes will be recorded as AEs.

An overview table will include the following:

- Number of TEAEs,
- Number and percentage of subjects with TEAEs,
- Number of drug related TEAEs,
- Number and percentage of subjects with drug related TEAEs,
- Number of serious TEAEs,
- Number and percentage of subjects with serious TEAEs,
- Number of serious drug related TEAEs,
- Number and percentage of subjects with serious drug related TEAEs,
- Number of TEAEs leading to permanent discontinuation of study drug,
- Number and percentage of subjects with TEAEs leading to permanent discontinuation of study drug, and
- Number of deaths.

The number and percentage of subjects with TEAEs, as classified by SOC, High Level Term (HLT), and PT will be summarized. Summaries will be provided for the following:

- TEAEs

- drug related TEAEs,
- serious TEAEs,
- drug related serious TEAEs,
- TEAEs leading to permanent discontinuation of study drug,
- drug related TEAEs leading to permanent discontinuation of study drug,

The number and percentage of subjects with TEAEs, as classified by SOC and PT will be summarized by time interval. For each adverse event in a particular interval, a subject will be counted if there is an onset of a treatment-emergent adverse event regardless of onset in other intervals.

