6.5.3 Liver Safety Assessment

The liver safety assessments will be summarized by the categories below based on the measurement from Alkaline Phosphatase (ALP), Alanine Transaminase (ALT), total bilirubin (TBIL), Aspartate Transaminase (AST), and their combination. These parameters will be based on measurements from a central laboratory.

The subjects highest value from Day 1 to Day 84 IA or Day 180 IM or EOT will be used. This criterion is without regards to the subjects baseline value.

- ALT > 3xULN, > 5xULN, > 10xULN, > 20xULN
- Total Bilirubin > 2xULN
- (ALT or AST > 3xULN) and Total Bilirubin > 2xULN
- (ALT or AST > 3xULN) and ALP < 2xULN and Total Bilirubin > 2xULN

The last 2 criteria to where 2 or more parameters are evaluated will be with the measurements on the same day or up to 1 day apart. The samples within 1 day to be considered. For example, if ALT is on day 10, ALP is on day 11 and TBIL is on day 12, this data should be considered. If ALT and ALP is on day 10, and TBIL is on day 11, this data should be considered.

The samples within 1 day apart can be used however the last criterion with 2 parameters, all 3 should be from the same day to be considered. For example, if ALT is on day 10

An eDish display plot of all patients will be created. The step-one eDISH including ALT alanine aminotransferase, TBL total bilirubin, eDISH evaluation of drug-induced serious hepatotoxicity, ULRR upper limit of reference range or normal will be created with all patients plotted.

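### The peak liver-value table in SAP 6.5.3 closes at end of treatment, so a category first crossed after the drug is stopped is not counted there, although adverse events count for 30 more days

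*SAP*

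**What the plan says.** **Liver table.** SAP 6.5.3 sets the window for the peak value: "The subjects highest value from Day 1 to Day 84 IA or Day 180 IM or EOT will be used". The categories are ALT above 3, 5, 10 and 20x ULN, total bilirubin above 2x ULN, and two rows that combine ALT or AST above 3x ULN with bilirubin above 2x ULN, one of them also requiring ALP below 2x ULN. The section also plans an eDISH plot, with no window of its own, and bases the parameters on a central laboratory.

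**EOT.** The protocol's key terms define it as: "The date the last dose of study drug was taken by the enrolled subject".

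**Adverse events.** SAP 6.5.1: "TEAE is defined as an AE observed after starting administration of the study drug through 30 days after EOT". Protocol 7.5.1 agrees: "TEAE is defined as an AE observed after starting administration of the study drug through 30 days after the last dose".

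**Stopping for liver findings.** Protocol Appendix 12.5 lists ALT/AST, bilirubin and INR findings under the words "Discontinuation of study treatment should be considered if".

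**Testing.** Footnote 11 to protocol Table 1 limits scheduled panels to the dosing period: "Hepatic panels will be collected at baseline, day 3, day 7 and then weekly thereafter while subjects are receiving study drug". Once an abnormality appears, Appendix 12.5 asks for repeat testing within 72 hours of notification. It then says that confirmed moderate abnormalities "should be repeated 2 to 3 times weekly then weekly or less if abnormalities stabilize or the study drug has been discontinued", and the sentence goes on to require that the child be asymptomatic. The 30- and 60-day follow-up "may be performed via telephone at the discretion of the investigator".

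**The concern.** The liver table and the adverse-event tables describe the same children over different periods. The shorter period ends on the day the drug stops, and for some children that day is chosen because liver values are rising. If a threshold is first crossed in the days after the last dose, the child is absent from that row of the liver table but can still be counted as having a treatment-emergent, possibly serious, adverse event.

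Protocol 1.4 singles out liver toxicity for close monitoring, and the combined enzyme-and-bilirubin rows correspond to the Hy's Law pattern described in Appendix 12.5. In a study of about 30 children, one case decides whether such a row reads zero. A maximum over a shorter window can only be equal or lower, so any error is toward fewer cases.

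**Working it through.** The plan states no liver-event rate, so there is no figure of its own to reproduce. The check compares the windows, then asks which values could fall between them, then shows what one such case would do to a row.

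**1. The gap.** The liver table ends at EOT, which is the last dose. TEAEs end at EOT + 30 days. Difference: (EOT + 30) − EOT = 30 days. For assumed last-dose days, the share of the TEAE window outside the liver table is 30/(stop day + 30):

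| Last dose (assumed) | Liver window, days | TEAE window, days | Share outside |
|---|---|---|---|
| Day 14 | 14 | 44 | 30/44 = 68% |
| Day 28 | 28 | 58 | 30/58 = 52% |
| Day 56 | 56 | 86 | 30/86 = 35% |
| Day 84 | 84 | 114 | 30/114 = 26% |

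**2. Are values expected in the gap?** None is scheduled: Table 1 has no panel at the follow-up visits. The source is Appendix 12.5. Over 30 days, weekly repeats give 30/7 ≈ 4 panels. Two to three a week give 60/7 ≈ 9 to 90/7 ≈ 13. After the drug is stopped, weekly or less applies once the child is asymptomatic, so about 4 or fewer is the more likely count in that state.

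**3. Does another table take them in?** No. SAP 6.5.2 summaries also end at Day 84 (or EOT), and shifts cover the treatment period. Listings have no stated time limit.

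**4. Which rows can lose a child?** Only those first crossed after EOT. A child stopped at ALT above 8x ULN is already in the 3x and 5x rows; the 10x and 20x rows and the bilirubin rows remain open. A child stopped because the combined pattern was already present is already in the combined row.

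**5. How often is a child stopped for liver enzymes?** Protocol 1.2 reports two withdrawals for adverse events among 27 children in the previous paediatric study, one of them for increased liver enzymes.

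- Rate: 1/27 = 3.7%, exact 95% CI 0.1% to 19.0%.
- Expected in 30: 30 × 1/27 = 1.1 (0.03 to 5.7 at the interval ends).
- Chance of at least one: 1 − (26/27)^30 = 68% (3% to 99.8%).

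This is a withdrawal rate, not a missed-case rate. The fraction f of such withdrawals that first cross a category after EOT is not given. Assuming f between 5% and 50%, the chance of at least one missed case is 1 − (1 − f/27)^30: 5% at f = 0.05 and 43% at f = 0.50.

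**6. Effect of one missed case on a row (exact 95% CI).**

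| N | Row as tabulated | Row with the case |
|---|---|---|
| 30 | 0/30: 0% (0 to 11.6%) | 1/30: 3.3% (0.1 to 17.2%) |
| 25 | 0/25: 0% (0 to 13.7%) | 1/25: 4.0% (0.1 to 20.4%) |

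N = 30 is the planned size; 25 is the minimum evaluable number in protocol 2.2.1.

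**The case against.** **The cut-off is not fully explicit.** The SAP sentence does not say which of its end points applies when they differ, so an early stopper's window might be run to Day 84 or 180. The EOT visit also has a ±7-day window, so a panel a few days after the last dose might count as EOT. Both points stand. Still, the protocol treats Day 84 or EOT as one end-of-treatment visit, so closing the window at EOT is the natural reading. Even the lenient reading leaves a child treated to Day 84 or 180 with no later cover beyond any visit window.

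**Such cases would be found anyway.** Potential Hy's Law cases are reported through the SAE route (protocol 5.5.1.2), clinically significant laboratory changes are recorded as AEs, the liver-abnormality CRF is completed, and a DSMB reviews safety. This stands as to detection. It does not make the table correct.

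**An on-treatment window matches the other laboratory summaries.** It does, and that is a reason to keep it, but not as the only window for a peak-value table.

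**Stronger readings that a reader might infer.**

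- That every post-stop peak and every bilirubin rise is lost. A rise before EOT is counted, and so is every category already met.
- That frequent testing continues after the drug stops, so later values are certain. The appendix says what should be done and relaxes the frequency for asymptomatic children off drug. Values are expected, not guaranteed.
- That 68% is the chance of a missed case. It is the chance of at least one liver-enzyme withdrawal, and it rests on a single event.

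**Conclusion.** The point holds in a limited form. SAP 6.5.3 closes 30 days before the TEAE window, and on the natural reading a child who first crosses a category in that gap is absent from that row. The children exposed to this are those stopped with rising enzymes, so the omission is not random and can only lower the count.

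The number of such children cannot be estimated from the documents. If there is one, a row reads 0/30 with an upper limit of 11.6% instead of 1/30 (3.3%; 0.1 to 17.2%). This assumes that the window ends at EOT, that the child is retested after stopping, and that the category was not already met. The study is descriptive, and the case should be visible elsewhere in the report. This is therefore a cheap improvement to a safety table, not a defect that undermines the trial's safety conclusions.

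**What to change.** In SAP 6.5.3:

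1. Tabulate the highest value after the first dose through 30 days after the last dose, including unscheduled tests and results from the liver-abnormality CRF.
2. Keep the on-treatment version in an adjacent column and state its end date without ambiguity.
3. State the same 30-day window for the eDISH plot.
4. Replace the central-laboratory basis with the local results that the protocol collects (protocol 5.4.2 and footnote 10 to Table 1). Otherwise the added results would conflict with the section's own source rule.
5. Because no panel is scheduled after EOT, footnote how many children had at least one liver test in the added 30 days.

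**Cost.** A few lines of SAP text, one extra table column and a footnote; no new visit, blood draw or change to treatment. The reported incidence may be slightly higher, and some values after the drug is stopped will have other causes, which the side-by-side columns help a reader to judge.

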3.3 Exclusion Criteria

Subject will be excluded from participation if any of the following apply:

1. Subject has familial short QT syndrome, is receiving medications that are known to shorten the QT interval, or has a clinically significant abnormal ECG.
2. Subject has evidence of hepatic dysfunction defined as any of the following:
 - Total bilirubin (TBL) ≥ 3 times the upper limit of normal (ULN)
 - Alanine transaminase (ALT) or aspartate transaminase (AST) ≥ 5 times the ULN
 - Known cirrhosis or chronic hepatic failure

3. Subject has used strong cytochrome P450 (CYP3A4) inhibitors or inducers such as ketoconazole, high dose ritonavir, rifampin/rifampicin, long acting barbiturates (e.g., phenytoin), carbamazepine and St. John's Wort in the 5 days prior to the first dose of study drug.
4. Subject has another IFI other than possible, probable or proven IA or IM.
5. Subject has chronic aspergillosis, aspergilloma or allergic bronchopulmonary aspergillosis.
6. Subject has received mould active systemic antifungal therapy, effective against the primary IMI, for more than 4 days during the 7 days preceding the first dose.

Note: Prior use of prophylactic antifungal therapy is acceptable. In case of breakthrough IA while on prophylactic mould-active azole class drugs, additional documentation will be required to be submitted to the sponsor medical monitor or designee to approve subject enrollment.

7. Subject has known history of allergy, hypersensitivity or any serious reaction to any of the azole class antifungals, or any components of the study drug formulation.
8. Subject has any condition, which, in the investigator's opinion, makes the subject unsuitable for study participation.
9. Subject is unlikely to survive 30 days in the investigator's opinion.
10. Subject has received investigational drug, with the exception of oncology drug trials, or trials with investigational drugs treating graft versus host disease, within 28 days or 5 half-lives, whichever is longer, prior to screening.

Waivers to the exclusion criteria will **NOT** be allowed.

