6.5.2 Clinical Laboratory Evaluation

Clinical laboratory samples will be collected and reported based on timepoints as listed in the Protocol Table 1 and Table 2 in Section 1 based on lab sample collection visits.

Clinical Laboratory variables will be created for each of the following:

| Chemistry: | Hematology: |
|--|--|
| Sodium | Red blood cells |
| Potassium | White blood cells (total leukocytes) |
| Magnesium | Hemoglobin |
| Calcium | Hematocrit |
| Chloride | Platelets (thrombocytes) |
| Glucose | Neutrophils (ANC) |
| Creatinine | Eosinophils |
| Creatine phosphokinase/Creatine kinase | Basophils |
| Alkaline phosphatase (ALP) | Lymphocytes |
| | Monocytes |
| | Blast cells |
| Hepatic Panel: | Pregnancy Test: |
| Albumin | Human chorionic gonadotropin (hCG) |
| Total bilirubin (TBL) | |
| Direct Bilirubin | |
| Total Protein | |
| Alanine aminotransferase (ALT) | |
| Aspartate aminotransferase (AST) | |
| | Other: |
| | Serum galactomannan (GM) |
| | Partial thromboplastin time/international normalized ratio (PTT/INR) |

The baseline value will be the last non-missing value taken on or prior to first dose of study drug. Quantitative values evaluated by the central laboratory including hematology and biochemistry will be summarized using mean, standard deviation, minimum, maximum and median at each analysis visit. Additionally, a within-subject change will be calculated as the post-baseline measurement minus the baseline measurement and summarized in the same

way. Clinical Laboratory data will be reported using the SAF population by Clinical Laboratory Tests collected at baseline and days 7, 28, 56 and 84 (or EOT).

Shifts relative to normal ranges from baseline to each time point during treatment period in lab tests will also be tabulated. Laboratory data will be displayed in listings. For quantitative laboratory measurements descriptive statistics will be used to summarize results and change from baseline for subjects.

Each laboratory result will be classified as low, normal, or high at each visit according to the laboratory supplied reference ranges as specified in the Protocol.

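### The SAP's liver categories ignore baseline, so four of the seven can count abnormality that the entry criteria allow before the first dose

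*SAP*

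**What the plan says.** SAP 6.5.3 (Liver Safety Assessment) defines the window and value as "The subjects highest value from Day 1 to Day 84 IA or Day 180 IM or EOT will be used", and adds "This criterion is without regards to the subjects baseline value". It has seven categories:

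- four for ALT: "ALT > 3xULN, > 5xULN, > 10xULN, > 20xULN";
- one for bilirubin: "Total Bilirubin > 2xULN";
- two combinations, both requiring ALT or AST above 3xULN with bilirubin above 2xULN, the second also requiring ALP below 2xULN.

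An eDISH plot of all patients is also planned, with no stated reference to baseline.

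Protocol 3.3, exclusion 2, sets the entry limits: "Alanine transaminase (ALT) or aspartate transaminase (AST) ≥ 5 times the ULN" and "Total bilirubin (TBL) ≥ 3 times the upper limit of normal (ULN"), together with known cirrhosis or chronic hepatic failure. Meeting any one of these excludes the child. There is no limit on the combination of enzyme and bilirubin, and none on ALP.

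SAP 6.5.2 (Clinical Laboratory Evaluation) covers the general laboratory summaries. They comprise descriptive statistics, change from baseline, and shifts for which "Each laboratory result will be classified as low, normal, or high at each visit". Baseline there is the last non-missing value on or before the first dose.

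**The concern.** The entry limits lie above several of the analysis thresholds. A child may be enrolled with a value that already meets a liver category, and a table that disregards baseline cannot show this. The window compounds the problem. It opens on Day 1 rather than after the first dose, and Protocol 2.2.1 lets screening run up to Day 1 before dosing, so a pre-dose sample can itself be the highest value.

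Safety is the first-listed objective, and Protocol 1.4 singles out liver toxicity for close monitoring. Protocol 7.4 confirms that there is no comparator group, so each child's own baseline is the natural reference for what changed on treatment. The SAP uses that reference for ECGs: section 6.5.5 tabulates changes from normal to abnormal and worsening by category in children with both baseline and later readings. The liver categories have no equivalent.

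**Working it through.** The plan states no rate or precision for the liver categories, so there is no figure to reproduce. The check has three steps.

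**1. Overlap of entry limits and thresholds.** The inputs are the limits in Protocol 3.3 and the categories in SAP 6.5.3.

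| SAP category | Values above the threshold admitted at entry | Can be met before dosing? |
|---|---|---|
| ALT > 3xULN | above 3 to below 5 | yes |
| ALT > 5xULN | none | no |
| ALT > 10xULN | none | no |
| ALT > 20xULN | none | no |
| TBL > 2xULN | above 2 to below 3 | yes |
| ALT or AST > 3x and TBL > 2x | both ranges above, together | yes |
| the same, with ALP < 2x | as above; ALP has no entry limit | yes |

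Four of seven categories overlap. The three higher ALT cut-offs do not, apart from a rise between the screening sample and the first dose.

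**2. How a pre-existing value reaches the table.** Protocol Table 1 schedules the hepatic panel at screening, day 3, day 7 and then weekly, with no separate Day 1 panel. There are two routes:

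- the screening sample is dated Day 1, so it falls inside the window; or
- the abnormality is still present on day 3 or a later panel.

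A value sampled before Day 1 that resolves by day 3 is not counted.

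**3. Size.** The planned number is about 30 (SAP 3).

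- One child contributes 1/30 = 3.3 percentage points to a category.
- With no new cases and one carried-over case, the table reads 1/30 = 3.3% (exact 95% CI 0.1 to 17.2). Counting only new crossings gives 0/30 = 0% (0 to 11.6).
- With two or three carried-over cases it reads 6.7% (0.8 to 22.1) or 10.0% (2.1 to 26.5).

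The documents do not say how many children enter above a threshold. Let p be that proportion for a given category, which is an assumption. The expected number is 30p, and the chance of at least one is 1 − (1 − p)^30.

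| Assumed p | Expected of 30 | Chance of at least one, n = 30 | Same, n = 25 |
|---|---|---|---|
| 1% | 0.3 | 26% | 22% |
| 5% | 1.5 | 79% | 72% |
| 10% | 3.0 | 96% | 93% |

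The n = 25 column uses the minimum number of evaluable subjects in Protocol 2.2.1. A combination category cannot be more common than either of its components, so smaller values of p are the relevant ones there.

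**The case against.** The case for leaving the section alone is that this is a descriptive table of highest values which openly declares that it ignores baseline. It calls no count treatment-emergent or drug-related. An inclusive screening table is a legitimate choice, and that point stands. It does not justify a window that can admit a pre-dose sample.

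Other material does bear on baseline. SAP 6.5.2 plans change from baseline, and all laboratory data are listed. Protocol 12.5 asks for a liver case report form with history and possible cause for confirmed abnormalities. Causality is judged through adverse event reporting. These sources let a reader trace an individual child, but none is a summary of who newly crossed a threshold. A child at 4xULN who stays there and one who rises to 15xULN both appear as high-to-high in the shift table, although the second would enter the >5x and >10x categories. Mean change does not identify crossings, and listings would have to be reworked by hand.

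Three stronger readings are tempting, and the documents do not support them:

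- A reader might infer that the table is bound to exaggerate drug-related liver injury. It can include carried-over cases, but only by the two routes above, and the number at entry is unknown.
- A reader might infer that a carried-over combination would be classified as Hy's Law. SAP 6.5.3 does not use that term, and Protocol 12.5 requires that no other explanation, including pre-existing liver disease, be found. The child meets a numeric screen only.
- A reader might infer that Protocol 12.5 contradicts exclusion 2, because an eligible child can exceed a monitoring threshold. An entry limit and an on-treatment monitoring threshold serve different purposes, so their overlap is not a contradiction.

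**Conclusion.** The point holds as a limit on what the liver table can show. Four of the seven categories can mix abnormality present before the first dose with abnormality that arose on treatment, and no planned summary tells them apart. With about 30 children and no control arm, each carried-over child can move a category by 3.3 percentage points.

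The overlap and the Day 1 window follow directly from the text. How often this will occur does not: the chances of 26% to 96% rest on an assumed prevalence at entry of 1% to 10%, and they count children above a threshold at entry, not all of whom need reach the table. A cheap improvement is warranted. The section does not misclassify anything under its own stated rule.

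**What to change.** Amend SAP 6.5.3 as follows:

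1. Use only values taken after the first dose, with the end of the window unchanged.
2. Keep the all-subjects row for each category. Beneath it, split the count by whether the last pre-dose value already exceeded that threshold. For the combinations, use whether the pre-dose values already met the same combination.
3. Mark children with elevated baseline values by a separate symbol on the eDISH plot.
4. Add a shift table of baseline against worst post-dose value in xULN bands for ALT, AST and bilirubin. Keep the existing shift relative to normal ranges, because Protocol 7.5.2 specifies it.

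The data are already collected. The cost is a few table rows, one extra table and one plot symbol. The treatment-emergent row has a slightly smaller denominator. For example, if one of 30 children is set aside, the exact upper 95% limit for zero events moves from 11.6% to 1 − 0.025^(1/29) = 11.9%.
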